8.6.2. Blinding

HORIZANT Extended-Release Tablets and placebo tablets will be identically matched in appearance and the bottle labels will not reveal the drug identity. The site investigator or designated approved study physician will make the decision to un-blind the identity of the investigational product in the event that the study blind needs to be broken to make medical decisions regarding subject treatment. If it is determined that unblinding is necessary to assess AEs or SAEs for expedited reporting, NIAAA may decide to request unblinding of a subject. Site staff or Sponsor's designee approved to un-blind the study drug will log into the IWRS to obtain the name of the investigational product to which the subject was randomized. The IWRS will automatically notify the un-blinded staff member at the Data Coordinating Center who will notify the Medical Monitor. NIAAA will be notified that an unblinding has occurred if unblinding has been performed by the investigator or medical monitor.

8.7. Interventions on Day -1 and Day 1

At study Day -1, after the subject is randomized, he/she will receive the first bottle of study drug and the instructional drug card to take home (Appendix 19.1). Site staff will explain the dosing plan to the subject (one tablet in the morning for the first 3 days, then one tablet in the morning and one in the evening for the next 4 days) and how to complete the drug card to track when tablets are taken. The subject will be instructed to take the first dose in the morning of Day 1 (expected to occur the day after the date of randomization). Subjects will be instructed to take tablets with meals and will be advised to avoid driving and operating heavy machinery, until they are aware of how the study drug affects them. The subject will watch the first module of Take Control (Day -1), will be given the schedule of visits, and the Week 2 visit will be scheduled.

Every study subject will be provided with a wallet card and instructed to carry this card that identifies the potential investigational products that s/he could be taking during the study. The card will provide the name and 24-hour phone number of the investigator (physician) at the site who can be contacted in the event of an emergency. The card will also instruct the non-study physician rendering emergency care to contact the study physician and inform him/her about the care.

If possible, clinic visits should be scheduled on the same day of the week that the subject received the first dose of study drug, but a 3-day window is allowed for conducting visits within the scheduled study week. Visits may be scheduled and conducted on any day of the week. Visits can be conducted outside of the scheduled study week, but only based upon subject request (e.g., for reasons related to patient non-compliance with the study schedule). Each subject will receive a visit schedule to take home for future reference

8.8. Weeks 1 and 2 Safety Telephone Contact

Midway through Weeks 1 and 2 subjects will be called for a safety assessment. The call during Week 1 should ideally be the day before the subject escalates their dose to 2 pills per day. Assessments will be the same as all other telephone contacts (see section 8.10).

8.9. Maintenance Phase

During Study Weeks 2 through 25 of the maintenance phase of the study, subjects will be seen in person at the clinical site 9 times and assessed by telephone 16 times. Week 26 is dose taper and there is a final clinic visit at Week 27 at the end of dose taper.

An alcohol breathalyzer will be administered at each visit, prior to any study assessments, to determine if the subject meets the BAC requirement of a BAC \leq 0.020 before proceeding with assessments. A urine drug test will be performed at each visit. At each of the clinic visits, subjects will meet with one or more study staff members who will systematically assess AEs since the last visit, take vital signs, administer questionnaires (CIWA-AR and C-SSRS), inquire about other medication use and assess drinking by TLFB. Clinical chemistry, pregnancy test for women of child-bearing potential and birth control methods (if female), blood for study drug compliance, and subject's weights will be collected in accordance with the schedule in Table 5. In addition, subjects will complete the battery of questionnaires in accordance with the schedule in Table 5.

Brief telephone assessments will occur weekly between in-clinic visits. The final in-clinic assessment will occur during Week 27. This visit should be scheduled after the subject takes the last dose of study drug.

Subjects will view a single module of Take Control that is expected to have a run-time of 10-15 minutes during each clinic visit. After completion of the Take Control module, a new supply of investigational product will be given and the bottle(s) from the previous period will be collected and a tablet count will be performed for accountability. Bottles with unused tablets will be returned to the subject. The dosing schedule will be reviewed and the subject will be provided instructions on how to complete the drug card to track tablet consumption. The subject will be instructed to bring the bottle(s) and drug cards with them to the next visit so the site staff can perform drug accountability (tablet counts). The subject will also be instructed to contact site staff if they are experiencing any intolerable AEs and are contemplating drug discontinuation.

Additional in-clinic visits are permitted under the protocol, if needed, due to the following circumstances: (1) the subject has concerns either about the medication or their drinking and wishes to be seen at a time other than their next scheduled in-clinic visit, or, (2) the subject has missed a visit and wishes to resume regular participation before their next scheduled visit, (3) the subject has reported some change in health, functioning, or circumstances which necessitate a visit to conduct safety assessments and evaluate the risk of continued participation in the trial, or (4) clinical laboratory measurements need to be repeated.

Subjects desiring additional counseling or professional therapy for non-crisis psychiatric matters (e.g., marital problems, work issues) should be encouraged to postpone such activity until their study participation is concluded. Attendance at self-help support groups (i.e., alcoholics anonymous) will neither be encouraged or discouraged. Any attendance at self-help support

groups will be recorded at the randomization visit and monthly in the Other Services Used for Alcohol Use Problems electronic case report form (eCRF).

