Primary: The primary outcome measure examines the hypothesis that HORIZANT Extended-Release Tablets will increase the PSNHDD compared to placebo during the last 4 weeks of the maintenance period (Study Weeks 22-25). A "heavy drinking day" is 4 or more drinks per drinking day for women and 5 or more drinks per drinking day for men. Drinking data will be collected by the Timeline Followback (TLFB) method. If during the last 4 weeks of the maintenance period of the study, the subject does not come back for clinic visits or provide TLFB data but agrees to telephone contact, then the subject will be asked if there were any heavy drinking days during the final study period. These data will be used to determine the primary efficacy endpoint when TLFB data are missing, otherwise the data will be imputed as having a heavy drinking day during this period.

Secondary: Secondary efficacy endpoints will also be analyzed over the last 4 weeks of treatment.

- 1. Percentage of subjects abstinent from alcohol (key secondary endpoint)
- 2. Percentage of subjects with a World Health Organization (WHO) drinking risk category decrease of:
 - a. at least 1-level
 - b. at least 2-levels
- 3. Percentage of days abstinent per week
- 4. Percentage of heavy drinking days per week
- 5. Weekly mean number of drinks per week
- 6. Weekly mean drinks per drinking day
- 7. Cigarettes smoked per week among smokers
- 8. Alcohol craving score [Alcohol Craving Scale Short Form (ACO-SR-R)]
- 9. Alcohol related consequences (ImBIBe) score
- 10. Pittsburg Sleep Quality Index (PSQI) score
- 11. Beck Anxiety Inventory (BAI) score
- 12. Beck Depression Inventory Scale II (BDI-II) score

Safety Endpoints Safety endpoints will be evaluated over the entire treatment and follow-up periods.

- 1. Vital signs
- 2. Blood chemistries
- 3. Urine drug screen results
- 4. Blood alcohol concentration (BAC) by breathalyzer
- 5. AEs
- 6. Electrocardiogram (ECG) results

- 7. Clinical Institute of Withdrawal Alcohol Revised (CIWA-AR) scores
- 8. Profile of Moods States (POMS) scores
- 9. Frequency of subjects with suicidal ideation at any time during the treatment period –Columbia-Suicide Severity Rating Scale (C-SSRS)

Compliance: Self report of compliance with investigational products and gabapentin plasma levels.

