(based on urinary recovery of gabapentin) for HORIZANT Extended-Release Tablets in the fed state is about 75%. Bioavailability under fasting conditions has been estimated by gabapentin urinary recovery to be 42% to 65%. In a food effect study, the exposure of gabapentin increased by 24%, 34%, and 44% with low, moderate, and high fat meals, respectively. The T_{max} of gabapentin after administration of 600 mg of HORIZANT Extended-Release Tablets was 5.0 hours in fasted subjects and 7.3 hours in fed subjects. Steady state is reached in 2 days with daily administration.

Metabolism: Neither HORIZANT Extended-Release Tablets nor gabapentin are substrates, inhibitors, or inducers of the major cytochrome P450 enzymes (CYP1A2, CYP2A6, CYP2B6, CYP2C8, CYP2C9, CYP2C19, CYP2D6, CYP2E1, and CYP3A4). HORIZANT Extended-Release Tablets is neither a substrate nor an inhibitor of P-glycoprotein *in vitro*.

4.3.4. **Drug Interactions**

Alcohol: Gabapentin enacarbil is released faster from HORIZANT Extended-Release Tablets in the presence of alcohol. This was determined in an in vitro dissolution study which was conducted to evaluate the impact of ethanol (5, 10, 20, and 40%) on the extended-release characteristics of HORIZANT Extended-Release Tablets. The in vitro study showed that about 63% of the total gabapentin dose was released at 1 hour at the highest alcohol level (40%), and about 43% of total drug was released at 1 hour with 5% alcohol. Ethanol causes a more rapid release of gabapentin enacarbil from the Extended-Release Tablets that may increase the risk for AEs associated with HORIZANT Extended-Release Tablets. Based on this data, consumption of alcohol is not recommended when taking HORIZANT Extended-Release Tablets.

Morphine: HORIZANT Extended-Release Tablets taken in conjunction with morphine causes increased somnolence/ sedation, dizziness, and nausea when compared with either drug alone. This was determined via the administration of a single 600 mg dose of HORIZANT Extended-Release Tablets 2 hours after a single 60 mg dose of extended-release morphine sulfate in 18 subjects and was associated with increased somnolence/sedation, dizziness and nausea for the combination compared to HORIZANT Extended-Release Tablets or morphine alone as measured by the visual analog scale. No changes in C_{max} and AUC of gabapentin, morphine or its active metabolite morphine-6-glucuronide were observed.

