HORIZANT for Alcohol Use Disorder Protocol Number: NCIG-006

	Scre	een	Ti- trate									Mair	itenan	ce								Taper		Safety Follow- up
Clinic Visit #	0	1		2		3		4		5		6		7		8		9		10		11	12	
Study Week	-2 to -1	Day -1	1	2	Mid week 2 & 3	4	5	6	7	8	9	10	11	12	13 - 15	16	17- 19	20	21- 23	24	25	26	EOS ^a /27	28- 29
BDI-II		X				X				X				X		X		X		X		X		
POMS		X				X				X				X		X		X		X		X		
Other Services Used for Alcohol Use Problems		X				X				X				X		X		X		X			X	

^a EOS=end of study. These assessments are to be done at Week 27 or if the subject discontinues early and agrees to a final clinic visit.

^b Test for opioids, cocaine, amphetamines, methamphetamine, tetrahydrocannabinol (THC), buprenorphine, methadone or benzodiazepines.

^c Only the AUD module is performed at Week 26.

^d AST, ALT, total bilirubin, creatinine, GGT.

^e Sitting blood pressure and heart rate.

f Only for subjects who consent to provide this sample.

^g For each subject, blood collections should be scheduled at different times relative to the morning dose at these 3 clinic visits.

^h Only SAEs will be reported from the time of signing informed consent until the first dose of investigational product administration. Thereafter, AEs and SAEs will be reported for the duration of the study.

ⁱ AEs, concomitant medications, CIWA-AR, and drug compliance reminder.

Only asked to subjects who are no longer participating in clinic visits and not willing to providing TLFB drinking data.

7. Study Interventions

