8.11. Final Clinic Visit

The final clinic visit occurs during Week 27; at which time the subject has completed taking investigational product. In addition to the assessments previously stated, subjects will have an Exit Interview assessment. The subject will be asked about their drinking for his/her impression of whether he/she was receiving active drug or placebo, if they felt that the medication helped drinking, how they would describe their experience taking the medication, if they would recommend it to a friend, if they would take it again if they needed further treatment in the future, and a question about desire to please people. The subject will be provided with a referral to a treatment program for their alcohol dependence. If a subject withdraws from the study early for any reason, the subject should be asked to return to the clinic for the conduct of all of the final clinic visit assessments.

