8.15. Subject Withdrawal or Discontinuation Procedures

Each subject has the right to withdraw consent and withdraw from the study at any time. In addition, the investigator may find it necessary to discontinue a subject for any reason, including the occurrence of an AE or noncompliance with the protocol.

In the event that a subject withdraws or is discontinued from the study, the reason(s) for the discontinuation from the study will be recorded and a pregnancy test (females only), body weight, vital signs measurement, ECG, clinical chemistry, C-SSRS, TLFB and an assessment of AEs will be performed as soon as possible after discontinuation from the study. Other assessments scheduled for the end of study visit will be collected if possible (Table 5). Additional blood samples for study drug measurement may be collected at the time of discontinuation from subjects who are discontinued due to AEs.

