12.4.4. Safety Analyses

AEs will be coded using the most recent version of the MedDRA and will be grouped by SOC and PT designation. The severity, frequency, and relationship of AEs to investigational product will be presented by SOC and PT groupings. Listings of each individual AE including start date, stop date, severity, relationship, outcome, and duration will be provided. Each AE (based on PT) will be counted once only for a given study subject. If the same AE occurred on multiple occasions, the highest severity will be assumed. Thus, study subjects are not counted multiple times in a given numerator in the calculation of frequencies for a specific AE. C-SSRS reports of suicidality or suicidal ideation will be reported as AEs and analyzed as AEs if the investigator determines after an interview with the subject that the responses are consistent with suicidal ideation or attempt.

Chemistry data, urine drug screen results, pregnancy test results, and alcohol breathalyzer results, will be reported as summary statistics. Vital signs will be presented as summary statistics and change from baseline. The proportions of ECG results considered abnormal and clinically significant will also be provided. CIWA-AR scores will be analyzed similar to the efficacy endpoints: mixed effects models with and without baseline characteristics. In addition, change from baseline (shift tables) will also be presented for clinical laboratory data. The numbers and proportion of subjects who reported CIWA-AR scores ≥ 10 at any time after the start of dosing will be presented.

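### For subjects who stay in the study, the only scheduled post-baseline ECG comes after the taper and last dose, so the ECG endpoint says almost nothing about the treatment period

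*Protocol*

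**What the plan says.** ECG results are the sixth safety endpoint. The Synopsis states: "Safety endpoints will be evaluated over the entire treatment and follow-up periods". Section 9.2 sets the same period for analysis. Section 12.4.4 gives the analysis: "The proportions of ECG results considered abnormal and clinically significant will also be provided".

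The ECG row of Table 5 has two marks, screening and EOS/Week 27. Footnote a says of the EOS column: "These assessments are to be done at Week 27 or if the subject discontinues early and agrees to a final clinic visit".

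On where Week 27 lies relative to dosing:
- Section 8.9: "Week 26 is dose taper and there is a final clinic visit at Week 27 at the end of dose taper", and of the final visit, "This visit should be scheduled after the subject takes the last dose of study drug".
- Section 8.11: "The final clinic visit occurs during Week 27; at which time the subject has completed taking investigational product".
- Table 7: Week 26 is one tablet a day, after 24 maintenance weeks at two a day.

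There is one other route to a post-baseline ECG. For subjects who withdraw or are discontinued from the study, Section 8.15 says: "vital signs measurement, ECG, clinical chemistry, C-SSRS, TLFB and an assessment of AEs will be performed as soon as possible after discontinuation from the study".

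**The concern.** The plan assigns the ECG endpoint to a period in which, for anyone who completes, no ECG is scheduled. Each completer contributes one recording before treatment and one after it. An effect that is present while the drug is present and fades with it would be missed in both arms alike.

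The ECG is out of line with the other objective safety measures. Table 5 puts vital signs and clinical chemistry at Weeks 4, 8, 12, 16, 20 and 24, all on maintenance. The Protocol gives no reason for treating the ECG differently.

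At stake is how a by-arm table of abnormal, clinically significant ECGs is read. Presented as covering treatment and follow-up, it could be taken as on-treatment evidence when it consists mostly of off-drug recordings. No analysis plan can repair this afterwards, because the recordings will not exist.

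**Working it through.** The Protocol gives no figure for the ECG endpoint, so none can be reproduced. The check is a count, a timing and a washout bound.

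**1. Scheduled on-drug ECGs.** In Table 5 the ECG row has no mark at Day -1, in titration, in maintenance (Weeks 2 to 25) or in the taper (Week 26). Count per subject remaining in the study: 0.

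**2. Other routes.**
- Leaving the study early (Section 8.15): the ECG can fall in any week and near dosing. Section 12.5 assumes 15% dropout, and 0.15 × 173 = 25.95, so at most about 26 per arm, and only if they attend.
- Stopping drug but staying in the study (Section 8.14.1.2): the ECG remains at Week 27, further from the last dose.
- Unscheduled safety visits (Section 8.9): allowed, but no ECG is specified.

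**3. Time from last tablet to an on-time Week 27 visit.** Table 6 gives 12 + 5×28 + 3×56 + 28 + 6 = 354 tablets. Table 7 gives 3×1 + 4×2 + 24×14 + 7×1 = 354, so the two agree. Of the 7 taper tablets, Table 6 has 6 used after Visit 11, so the first is taken on the morning of that visit. The last falls on the morning of the day before Visit 12, one week later: about 24 hours. Section 8.7 allows a 3-day window, so a late visit is about 24 + 72 = 96 hours after the last tablet.

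**4. Residual exposure.** The Protocol gives no half-life for this product. Section 4.3.3 says: "Steady state is reached in 2 days with daily administration". If that means 4 half-lives, the half-life is 48/4 = 12 h; I assume a range of 6 to 12 h. Tmax is varied from 0 (immediate absorption) to 7.3 h (the fed value in Section 4.3.3). The model has one compartment, with the once-daily taper at steady state.

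The maintenance average is 2 doses per 24 h. The ratio of the concentration *t* hours after the last tablet to that average is

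R(t) = 12k · [ka/(ka − k)] · [e^(−kt)/(1 − e^(−24k)) − e^(−ka·t)/(1 − e^(−24ka))], with k = ln 2 / half-life,

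where ka solves ln(ka/k)/(ka − k) = Tmax. With immediate absorption this reduces to 12k·e^(−kt)/(1 − e^(−24k)).

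- Low end at 24 h (half-life 6 h, Tmax 0): 12 × 0.1155 × 0.0625/0.9375 = 0.092.
- High end at 24 h (half-life 12 h, Tmax 7.3 h, ka = 0.268): 0.693 × 1.275 × (0.3333 − 0.0016) = 0.293.

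| Hours after last tablet | Share of maintenance average |
|---|---|
| 24 | 9% to 29% |
| 48 | 0.6% to 7.4% |
| 96 | 0.5% or less |

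**5. Dilution, for illustration only.** The event rates here are assumed. If an effect shows only in the 15% who leave early, the arm difference shrinks to 0.15 of its size: 2% versus 8% becomes 2% versus 2.9%, and 5% versus 15% becomes 5% versus 6.5%. With 173 per arm and two-sided 0.05, power falls from about 73% to 8% and from about 88% to 9%. The Protocol plans no ECG test, so this is only a yardstick.

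**The case against.** **The stronger reading.** A reader might infer that Week 27 is the only post-baseline ECG for anyone and that the endpoint cannot show a drug effect. The Protocol does not support that. Section 8.15 and Table 5 footnote a yield ECGs at early withdrawal, some possibly close to dosing. A lasting change, or residual drug at an on-time visit, could also show.

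**The stated period.** Treatment and follow-up is one umbrella phrase over nine endpoints and does not promise that each is measured on drug. That is a fair reading of the wording, so this is not a flat contradiction. It still leaves the treatment period without ECG data for those who stay.

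**Prior evidence.** Section 4.3.15 reports no clinically relevant QTc prolongation at 6,000 mg and more than 2,300 patients treated. This stands and lowers the clinical weight. A reader might try to set it aside because alcohol speeds release from the tablet (Section 4.3.4). That argument does not work: faster release cannot deliver more than the 600 mg in a tablet, one-tenth of 6,000 mg, and the full daily 1,200 mg is one-fifth. Section 4.3.4 names no cardiac signal.

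**Other cover.** Adverse events and vital signs are followed on treatment, and no ECG hypothesis or between-arm test is planned. True, but neither replaces an ECG, and Section 12.4.4 still reports the proportions.

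**The washout range.** It rests on an assumed half-life, and the planned case is about 24 hours, not 4 days. Accepted: at 24 hours up to about 30% of average exposure may remain.

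**Conclusion.** The point holds for subjects who remain in the study. They have no scheduled ECG on the maintenance dose. Their single post-baseline ECG is taken at roughly 10 to 30% of maintenance exposure if the visit is on time and at a negligible level if it is 4 days after the last tablet. The ECG endpoint therefore has very low sensitivity to an acute, reversible effect and does not describe the treatment period named in Section 9.2. The early-withdrawal ECGs, about 26 per arm at most, are a partial exception.

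The count of zero comes straight from Table 5 and needs no assumption. The exposure range assumes a half-life of 6 to 12 h and one-compartment kinetics; a longer half-life would raise it. The figure of 26 assumes the planned 15% dropout and full attendance.

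This is not evidence of an unrecognised cardiac risk, and the documents do not support reading it that way. It is an inexpensive improvement of modest clinical weight.

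**What to change.** In Table 5, move the scheduled post-baseline ECG from EOS/Week 27 to Visit 10 (Week 24), an existing maintenance visit at which blood for gabapentin levels is already drawn. Keep the Section 8.15 ECG for every subject who withdraws from the study, at whatever week; footnote a and Section 8.11 need matching wording. In Section 12.4.4, summarise the Week 24 ECG against screening by arm and flag subjects already off drug at Week 24, since those who stop drug stay in the study.

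Cost: one moved cell, short text changes and a slightly longer Visit 10, with no additional scheduled ECG. Completers would have no end-of-study ECG, so an abnormality that persists or appears late would not be recorded.

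If the schedule cannot change, Sections 9.2 and 12.4.4 should describe the ECG as a post-treatment assessment that does not inform on-treatment ECG safety, with early-withdrawal ECGs shown separately.
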